5.0 Statistical Analysis and Endpoints

5.1 Sample Size and Primary Endpoint:

Population: Acutely decompensated heart failure patients with or at risk for diuretic resistance or congestive nephropathy.

Hypothesis: Use of oral sodium chloride will lead to increased fluid volume removal and attenuate diuretic related renal dysfunction.

Study Design: Prospective, randomized, double blind, placebo controlled, single-center study

Endpoint: Net change in weight and change in creatinine from baseline to 96 hours after initiation of sodium chloride capsule supplementation [or discharge] vs placebo (as analyzed by intention to treat)

Power: 80% (2-sided alpha 0.05)

Sample Size Estimate: 85

Trial	Endpoint	SD	alpha	Power	Difference	Sample size
UNLOAD	Wt change (kg)	3.5	0.5	80	2.2	80
DOSE	Wt change (kg)	4	0.5	80	2.2	104
CARESS-HF	Wt change (kg)	5.1	0.5	80	2.2	168
ATHENA-HF	Wt change (kg)	3.4	0.5	80	2.2	74
Aliti	Wt change (kg)	2.85	0.5	80	2.2	52
3T	Wt change (kg)	2.7	0.5	80	2.2	48
AVERAGE		3.77	0.5	80	2.2	84
<hr/>						
UNLOAD	Cr change (mg/dl)	0.6	0.5	80	0.3	126
CARESS-HF	Cr change (mg/dl)	0.53	0.5	80	0.3	98
Athena-HF	Cr change (mg/dl)	0.3	0.5	80	0.3	32
AVERAGE		0.476	0.5	80	0.3	80

Based on data from the above clinical trials which evaluated diuretic strategies in decompensated heart failure, we believe that 85 patients will give us 80% power to detect a 2.2 kg (5 lb) difference in weight and a 0.3mg/dl difference in serum creatinine levels at 96 hours.

5.2 Safety Endpoints

1. Initiation of dialysis or RRT.
2. Need for mechanical intubation or new initiation of positive pressure ventilation.
3. Need for IV vasoactive medications
4. ICU transfer
5. Death

5.4 Analytical Plan

See above

6.0 Safety Reporting

6.1 Adverse Events

An adverse event (AE) is any event, side effect, or untoward medical occurrence in a subject in a clinical trial whether or not it is considered to have a causal relationship to the study drug, device or procedure. An AE can therefore be any unfavorable and unintended sign, symptom, laboratory findings outside of normal range, physical examination finding, or disease temporally associated with the use of the study drug, device or procedure whether or not the event is considered related to the study drug, device or procedure. Tracking of adverse events will be done after randomization.

6.1.2 Serious Adverse Events

Adverse events are classified as serious or non-serious. A *serious adverse event* is defined as any adverse event occurring that results in any of the following outcomes:

- 1) Death
- 2) ICU transfer
- 3) Respiratory failure
- 4) Initiation of renal replacement therapy
- 5) A persistent or significant disability or incapacity

Important medical events that may not result in death, be life-threatening, or require hospitalization may be considered a serious adverse event when, based upon appropriate medical judgment, they may jeopardize the patient or subject and may require medical or surgical intervention to prevent one of the outcomes listed in this definition.

6.1.3 Documenting and Reporting of Adverse Events

Adverse events reporting will begin from the time the patient is randomized until the subject has completed the final study visit.

For the purposes of this study, adverse events that are in the opinion of the investigator clinically significant will be tracked including hyperkalemia, acute kidney injury, and hypotension requiring cessation of drug.

7.0 Administration

7.1 Maintaining the Security of Patient Data

Data will be stored on a REDCAP database. There is an instance of this database maintained as a resource at Cleveland Clinic. REDCAP is maintained by Cleveland Clinic but is accessible on and off campus in secure fashion. The data will be entered into the database after completion of study procedures. This data will be entered into REDCap by the investigators. The study principle investigator, co-investigators, statistician(s) and study monitoring staff are the only individuals that will have permission to access the data, and will be able to do so by request.

7.1.1 Data Collection

Demographic and clinical variables will be extracted from the electronic medical record. Adverse event information will be provided by the patient and verified by medical record review/record request if from outside the facility. A RedCap database will be built with eCRFs used to collect study information. Patients will be identified in the EDC by their RedCap assigned record ID. Database maintenance will be delegated to members of the study team.

Variables to be collected: For complete data collection, a REDCAP data-dictionary is included in IRB submission

Hospitalization:

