- Length of index hospitalization [timepoint: enrollment to discharge]
- Heart failure rehospitalizations, unscheduled clinic and emergency department visits [timepoint: discharge to 30 days post discharge]
- Death from any cause [timepoint: enrollment to 90 days post enrollment]
- Initiation of renal replacement therapy or ultrafiltration [timepoint: enrollment to 90 days post enrollment]
- Occurrence of a serious adverse event [timepoint: enrollment to 90 days post enrollment]

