8.1 Safety Monitoring

An internal Data Safety Monitoring committee will be comprised of Cleveland Clinic physicians who are not participating in the study as they do not rotate in inpatient clinical services or only practice in the intensive care settings (outside of the study cohort): [name] MD, Chair of the DSM committee, and members including [name] PharmD, and [name] MPH. Participant safety will be protected and monitored during the entire study period during their hospital admission and by 90-day phone calls to the patients. There will be a biweekly review of the safety and tolerability outcome measures by the study coordinator. These safety and tolerability outcomes and any other adverse events that occur will be recorded in the patient's electronic medical record. Any adverse events that occur will be investigated to identify possible etiology and relationship to study procedures and reported to the IRB and the DSM committee within 10 working days of their discovery, with the exception of any deaths, which will be reported within 5 working days of their discovery.

Data Base-Case Report Form Completion

Only site staff listed on the Signature and Delegation Log are authorized to enter data or make corrections to CRFs/CRF review will include review for legibility, completeness and consistency with source documents. CRFs should be completed on all subjects that have been randomized.

REFERENCES:

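### Post-discharge adverse events originate from the patient's own report, and no independent source is named for 90-day death, renal replacement therapy and serious adverse events

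*Combined protocol and SAP*

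**What the plan says.** Section 7.1.1 names two sources in consecutive sentences. The first reads "Demographic and clinical variables will be extracted from the electronic medical record". The second treats adverse events differently: "Adverse event information will be provided by the patient and verified by medical record review/record request if from outside the facility".

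The secondary endpoints in section 1.1 include "Death from any cause [timepoint: enrollment to 90 days post enrollment", "Initiation of renal replacement therapy or ultrafiltration [timepoint: enrollment to 90 days post enrollment" and "Occurrence of a serious adverse event [timepoint: enrollment to 90 days post enrollment" (closing brackets omitted). Section 6.1.2 counts death, ICU transfer, "Respiratory failure" and initiation of RRT among the SAEs. Section 5.2 separately lists ICU transfer and "Need for mechanical intubation or new initiation of positive pressure ventilation" as safety endpoints, with no time window.

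Section 8.1 says that safety is monitored during the admission and "by 90-day phone calls to the patients". The follow-up list in 7.1.1 has a heart failure visit within 4 weeks, if one takes place in routine care, and a call labelled 30+ day.

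**The concern.** For adverse events the patient starts the process and the record confirms what the patient said. That order suits symptoms. It does not suit an endpoint such as death, where the patient cannot be the informant, and it is fragile when the patient is ventilated or in another hospital at the time of the call. If there is no report, the text gives nothing to verify and no prompt to request outside records.

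The 90-day safety outcomes are at stake. Failure to reach a patient is plausibly related to the outcome, so the events lost would not be a random subset. Section 1.2 states safety as an aim alongside efficacy, and in a trial of 85 patients a few missed events could change the safety comparison. The primary endpoint is measured at 96 hours or discharge and is not affected.

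**Working it through.** The plan states no event rate, loss rate or ascertainment figure, so there is no figure to reproduce. The check is to read the sections together and follow each kind of event.

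**Which outcomes run past discharge.** Death, RRT/ultrafiltration and SAEs run explicitly to 90 days (1.1). ICU transfer and respiratory failure reach 90 days only through the SAE definition (6.1.2). The ventilation item in 5.2 has no window and reaches 90 days only where it meets that definition.

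**What happens to each kind of event if the text is followed.**
- *Event during the index admission:* it is visible in the chart, and the 4.1 schedule collects adverse events at every inpatient time point from Day 1. No gap.
- *Non-fatal event after discharge, patient reached later:* the patient reports it and the record verifies it. No gap.
- *Non-fatal event at the trial centre, patient not reached:* it is in the centre's record, but no step tells staff to look there.
- *Non-fatal event elsewhere, patient not reached:* there is no report, so nothing prompts a record request.
- *Death after discharge:* the patient cannot report it, and no other source is named.

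**Whether another provision closes the gap.**
- Section 8.0 reviews SAEs and endpoints for all subjects. It names no source and sits beside verification of entered data.
- Section 8.1 has the coordinator review safety outcomes every two weeks, again with no source named.
- Section 6.1.3 runs adverse event reporting to the final study visit and does not say what happens if that contact fails.
- Section 5.4 only refers back to earlier text, which contains no rule for unknown 90-day status.
- The adverse events named for the hospitalization and the follow-up visit in 7.1.1 are hyperkalemia, angioedema, acute kidney injury and hypotension. Death, RRT, ICU transfer and ventilation are not named there.

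**Timing of the call.** The 4.1 schedule has one follow-up call column. Section 7.1.1 labels the call 30+ day, and section 8.1 speaks of 90-day calls. A call made soon after day 30 would satisfy the first label and could not cover endpoints to day 90.

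**Illustration, on assumptions only.** Let r be the 90-day event risk and m the share of events missed. Recorded events = 85 × r × (1 − m), with 85 from section 5.1.

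| r (assumed) | True events | m = 25% | m = 50% |
|---|---|---|---|
| 5% | 85 × 0.05 = 4.25 | 3.2 | 2.1 |
| 15% | 85 × 0.15 = 12.75 | 9.6 | 6.4 |

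For two arms, assume equal allocation (85 / 2 = 42.5 per arm), true risks of 15% and 5%, and m = 50% in both arms:
- True events: 42.5 × 0.15 = 6.4 and 42.5 × 0.05 = 2.1.
- Recorded events: 3.2 and 1.1, or risks of 7.5% and 2.5%.
- Risk difference: 15 − 5 = 10 points becomes 7.5 − 2.5 = 5 points.
- Risk ratio: 15 / 5 = 3 and 7.5 / 2.5 = 3, so it is unchanged.

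Each patient of unknown status can move an arm's risk by 1 / 42.5, about 2.4 percentage points.

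**The case against.** The strongest reply is that one loosely worded sentence is being read too literally. Section 6.1 defines adverse events to include laboratory and examination findings, and the tracked events include hyperkalemia and acute kidney injury, which patients cannot report themselves. Section 8.1 sets a reporting deadline for deaths counted from their discovery, so the protocol expects deaths to be learned of somehow. Section 8.0 covers endpoints as well as SAEs for all subjects, which takes in patients with no reported event. Section 7.1.1 also defers full data collection to a REDCap data dictionary. Neither that dictionary nor the consent form is in the text available here, so an alternate contact or vital-status field may already exist.

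Much of this stands. It rules out four stronger readings that a reader might infer:
- *That the patient is the only source of all safety data.* The inpatient record plainly contributes.
- *That the gravest events in general are the ones most likely to be missed.* The inference is sound for death. It is not shown for dialysis, ICU care or ventilation, which a survivor can report later and which are charted if they occur at the centre.
- *That the plan counts unreached patients as event-free.* No section says so. The plan is silent.
- *That the treatment comparison is necessarily biased toward no difference.* With equal proportional loss, the ratio is preserved while the absolute difference and the information shrink. Whether loss would differ by arm cannot be judged from the documents, and the plan makes no formal claim of demonstrated safety.

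What the reply does not supply is a named way to find an unreported event after discharge, or a rule for patients whose 90-day status is unknown.

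**Conclusion.** The point holds in limited form. The stated method starts from patient report and, after discharge, from calls to patients, while three endpoint groups run to day 90. Followed as written, it may leave post-discharge deaths unrecorded, along with events in patients who cannot be reached. The case is clearest for death and weaker for non-fatal events. The existing reviews reduce the risk but do not describe a search.

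The size of the under-count cannot be derived from the documents. The event risks of 5% to 15%, the missed shares of 25% and 50%, the 15% versus 5% contrast and equal allocation are all assumptions. They show only that event counts would be small and that a few misses would matter. The consequence is confined to secondary and safety outcomes. An amendment is worthwhile because the better method is specific and cheap.

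**What to change.** Amend 7.1.1 and 8.1 as follows.
- For every randomized patient, whether or not the call is answered, study staff review the medical record through day 90 post enrollment for death, RRT/ultrafiltration and SAEs. They record vital status and the last-known-alive date.
- The patient call supplements this for events at other facilities. An alternate contact is used if the patient is not reached.
- The number of patients with unknown 90-day status is reported by arm, and these patients are not counted as event-free.
- Because loss is likely to be informative, censoring at last contact is not sufficient alone. Any censored analysis is accompanied by a best/worst-case sensitivity analysis, with unknowns counted as events in one arm only and then in the other arm only.
- The 30+ day call in 7.1.1 and the 90-day calls in 8.1 are reconciled, so that the contact supporting the 90-day endpoints covers the whole window.

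The cost is about 85 brief chart reviews by existing staff and one amendment, plus an alternate-contact field if none exists. No new visit or test is needed.

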1. MRN
2. Sex
3. Age
4. Race/Ethnicity
5. Date of admission
6. Date of discharge
7. Date of Randomization and Medication administration
8. Length of Hospital Stay (in days)
9. Labs: CMP, CBC
10. Imaging: EF by echo, Other echo parameters for valve function, RV function, and chamber dilation
11. NT-Pro-BNP at admission and discharge and 30 day followup
12. Heart Failure Classification (Ischemic, Non-Ischemic)
13. Non-invasive blood pressure (SBP/DBP MAP), Fluid balance, Urine output/Fluid intake at Admission, Day 1-5, discharge and followup
14. Medical history
15. Concomitant Medications
16. Use of temporary mechanical support, IV vasoactive medications
17. Adverse events (hyperkalemia, angioedema, acute kidney injury, sustained hypotension requiring cessation of drug)
18. Diet Order

Any HF Follow-Up Visit Within 4 Weeks (as part of routine clinical care)

1. NT-proBNP

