1.0 INTRODUCTION

1.1 Purpose of this Study:

We are proposing a prospective, randomized, double blinded, placebo-controlled single center study evaluating the role of co-administration of oral sodium chloride with intravenous diuretics in patients hospitalized with acute decompensated heart failure. We are approaching this study with the hypothesis that the use of oral sodium chloride leads to improved effective diuresis (as measured by weight loss) and renal function as compared to placebo in patients hospitalized with acute decompensated heart failure undergoing aggressive intravenous diuretic therapy.

Primary endpoint:

[figure not shown]
Our primary outcome will be a composite outcome of change in weight and change in creatinine from baseline to 96 hours (or discharge) after initiation of sodium chloride capsule administration vs placebo (as analyzed by intention to treat)

The bivariate outcome will be displayed on a two-dimensional grid with individual data points for each patient representing paired changes in both creatinine and weight at 96 hours after randomization (or at discharge) (Fig. 1). A confidence region for the average difference between treatment arms in this bivariate response will be described as an ellipse, and the two treatment arms will be compared with the use of the Hotelling T-square test, which is a multivariate analog of the 2-sample t test used with a single continuous variable.

The null hypothesis is that there is no difference between the treatment groups in this 2-dimensional end point.

Secondary endpoints:

- Change in creatinine [timepoint: enrollment to 96 hours (or discharge)],
- Change in weight [timepoint: enrollment to 96 hours (or discharge)]
- Change in daily urine output [timepoint: day of enrollment, active treatment days 1, 2, 3, 4],
- Change in serum sodium [timepoint: day of enrollment, active treatment days 1, 2, 3, 4],
- Change in thirst distress survey [timepoint: enrollment to 96 hours (or discharge), followup phone call],
- Time to discontinuation of intravenous diuretic therapy [timepoint: enrollment to discharge]
- Total diuretic dosage in oral furosemide equivalents [timepoint: enrollment to 96 hours (or discharge)],
- Daily urine output/daily total furosemide dose [timepoint: day of enrollment, active treatment days 1, 2, 3, 4]
- Guideline directed medical therapy [timepoint: enrollment to discharge]

- Total potassium supplementation required [timepoint: enrollment to 96 hours or discharge]

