
2.1 Inclusion/Exclusion Criteria

Inclusion Criteria:

- Age \geq 18 years old AND
- Admitted to cardiology floor (non-ICU) with primary diagnosis of decompensated heart failure AND
- NT-proBNP >1000 ng/L AND
- Initiation of continuous furosemide infusion at a rate of 10mg/hr or higher.

Exclusion Criteria:

- Serum sodium (Na⁺) level less than 120 or greater than 145.
- Average systolic blood pressure >180 mmHg or DBP >100 mmHg over past 24 hours.
- Anticipated length of stay less than 72 hours.
- Use of vasopressin antagonist
- Current use of sodium chloride tablets.
- Active diagnosis of diabetes insipidus
- Inability to tolerate oral diet or swallow pills
- Presence of malabsorptive gastrointestinal disorder (Crohn's disease, short gut syndrome)
- The use of iodinated radiocontrast material in the past 72 hours or anticipated use of intravenous contrast during the current hospitalization
- Admission with intention to undergo open heart surgery.
- Use of intravenous inotropes, vasopressors or vasodilators at enrollment
- A baseline estimated glomerular filtration rate <15 mL/min/1.73m² according to the Chronic Kidney Disease Epidemiology Collaboration (CKD-EPI) formula at the moment of inclusion
- Use of renal replacement therapy at time of enrollment.

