4.1 Study Evaluations

All study evaluations will be as per clinical standard of care. Research procedures will include the randomization of sodium chloride vs placebo as well as adverse event reporting.

Study Procedures	Time Point 1 Screening/ Enrollment	Time Point 2 Salt vs Placebo Day 1	Time Point 3 Salt vs Placebo Day 2	Time Point 4 Salt vs Placebo Day 3	Time Point 5 Salt vs Placebo Day 4	Time Point 6 Active Treatment Completion Day 5	Time Point 7 Discharge	Time Point 8 Outpatient followup (routine)	Timepoint 9 Followup Phonecall
Informed Consent and Randomization	x								
Collection of baseline characteristics from medical	x								

record (prior medications, PMH, demographics, EF, baseline /admission labs)									
Administer Thirst Distress Survey	x					x			
Vitals and 24 Hour Fluid Balance (Intake/Output)	x	x	x	x	x	x	x	x	
Administration of Salt vs Placebo (2g TID w/ meals)		x	x	x	x				
Collection of Urine electrolytes		x	x	x	x	x	x		
BMP/NT-ProBNP (per usual clinical care)	x	x	x	x	x	x	x	x	
Review of Current Medications and Diet Order	x	x	x	x	x	x	x	x	
Blood draw for biomarker analysis*		x				x			
Adverse Events		x	x	x	x	x	x	x	x
Reason for discontinuation of study drug			x	x	x	x			
Length of hospital stay							x		
Phone Contact Readmission?									x

* Blood draws for biomarker analysis will be limited to the first 50 patients enrolled.

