2. CMP
3. Current Medications
4. Non-invasive blood pressure (SBP/DSP), weight
5. Concomitant Medications
6. Adverse Events (hyperkalemia, angioedema, acute kidney injury, sustained hypotension requiring cessation of drug)

30+ day phone call

1. 30 day readmission
2. Adverse Events

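### The named adverse events fit an oral sodium chloride load poorly: hypernatremia, hypertension and worsening congestion are not predefined as adverse events or safety endpoints

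*Combined protocol and SAP*

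**What the plan says.** The intervention is a salt load. The schedule in Section 4.1 reads "Administration of Salt vs Placebo (2g TID w/ meals" and marks it on Days 1 to 4. Section 1.2 gives the study's purpose as evaluating both efficacy and safety.

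Adverse events are described in four places:

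- Section 6.1 defines them broadly, to cover any "unfavorable and unintended sign, symptom, laboratory findings outside of normal range", whether or not related to study drug.
- Section 6.1.3 narrows this to events that the investigator considers clinically important, which "will be tracked including hyperkalemia, acute kidney injury, and hypotension requiring cessation of drug".
- Section 7.1.1, hospitalization variables, item 17: "Adverse events (hyperkalemia, angioedema, acute kidney injury, sustained hypotension requiring cessation of drug".
- Section 7.1.1, follow-up visit, item 6: "Adverse Events (hyperkalemia, angioedema, acute kidney injury, sustained hypotension requiring cessation of drug".

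Section 7.1.1 also says that adverse event information comes from the patient and is verified against medical records, and that the complete field list is in a REDCap data dictionary submitted to the IRB. Section 8.1 sends any adverse event to the IRB and the safety committee within 10 working days, or 5 for deaths. The analytical plan in Section 5.4 only points back to earlier text.

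**The concern.** In congested patients given extra sodium chloride, one would look first for sodium rising above range, blood pressure rising and congestion getting worse. None of these is a named event. Angioedema is the clearest misfit among the terms that are named. Hyperkalemia and hypotension are reasonable background risks during aggressive diuresis, but they are not the events one would first attribute to a salt load.

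Section 2.1 already sets entry limits on the quantities in question. It excludes serum sodium above 145, and also "Average systolic blood pressure >180 mmHg or DBP >100 mmHg over past 24 hours". There is no matching named event once dosing starts.

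What is at stake is how the safety result can be read. If events are gathered mainly under the listed terms, the arms are compared largely on events the capsules are unlikely to cause. A clean-looking table would then say little about the harms a clinician would ask about.

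**Working it through.** No figure in the plan needs reproducing. The check sets the lists, the data and the reporting route side by side.

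**1. Size of the load.** 2 g × 3 doses = 6 g/day. 6 g × 4 treatment days = 24 g in total.

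**2. Where the three events are named.**

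| List | Hypernatremia | Hypertension | Worsening congestion |
|---|---|---|---|
| 6.1.3 tracked events | no | no | no |
| 7.1.1 hospitalization, item 17 | no | no | no |
| 7.1.1 follow-up visit, item 6 | no | no | no |
| 5.2 safety endpoints | no | no | only severe consequences (ventilation, ICU transfer) |
| 6.1.2 serious outcomes | no | no | only severe consequences (respiratory failure, ICU transfer) |

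That is 5 lists × 3 events = 15 cells, and none of the 15 names the event. The lists also differ among themselves: angioedema is in both 7.1.1 lists but not in 6.1.3, and hypotension is qualified as sustained only in 7.1.1.

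**3. What is measured.**

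- Sodium: a secondary endpoint, "Change in serum sodium [timepoint: day of enrollment, active treatment days 1, 2, 3, 4". The laboratory row of the schedule is "BMP/NT-ProBNP (per usual clinical care", so the draws follow routine practice.
- Blood pressure and fluid balance: recorded at admission, on Days 1 to 5, at discharge and at follow-up (7.1.1).
- Weight: half of the primary outcome, as one change from baseline to 96 hours or discharge (1.1).
- Heart failure readmissions and unplanned visits: a secondary endpoint to 30 days after discharge (1.1).

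**4. Why measurement alone does not give event counts.**

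- Entry sodium runs from 120 to 145, a span of 145 − 120 = 25. A patient entering at 120 could rise by up to 25 and stay within the entry range, while a patient entering at 145 leaves it with any rise. A mean change pools the two and does not show who went above range.
- A single change in weight does not identify a patient who got worse in hospital and then recovered.
- A patient cannot report a laboratory value or a symptomless rise in blood pressure, yet 7.1.1 makes the patient the source of adverse event information, with the record used to verify it.
- The committee route in 8.1 starts from an adverse event. If nobody classifies a sodium or blood pressure excursion as one, it has no stated path to the committee.
- Occurrence of a serious adverse event is a secondary endpoint, but no section describes a summary of adverse events by term and arm.

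**5. Scale, by assumption only.** The plan gives no rates and no allocation ratio. With equal allocation, 85 / 2 = 42.5, so 42 or 43 patients take active capsules. The expected number of events is the number of patients × the assumed rate:

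- 5%: 42 × 0.05 = 2.1
- 10%: 42 × 0.10 = 4.2 to 43 × 0.10 = 4.3
- 20%: 43 × 0.20 = 8.6

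Rates of 5% to 20% thus mean about 2 to 9 active-arm events whose recording depends on individual judgment. The point does not rest on any of these rates.

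**The case against.** The strongest reply is that the plan already covers these harms. Section 6.1 takes in abnormal laboratory values and signs. The list in 6.1.3 is illustrative, because it is introduced as an inclusion. Serum sodium and weight change are outcomes to be compared between arms. Blood pressure and fluid balance are recorded throughout. Section 8.1 sends any adverse event, serious or not, to the committee and adds a biweekly safety review. Section 6.1.2 allows for important medical events, and the schedule records why study drug was stopped.

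Much of this stands, and it rules out several stronger readings that a reader might infer:

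- *That these harms are not tracked at all.* The underlying sodium, blood pressure, fluid balance and weight data are collected.
- *That the lists are closed and no field exists.* The complete data dictionary is outside these documents, so this cannot be established.
- *That the committee would hear only of ICU transfer, respiratory failure, renal replacement or death.* Section 8.1 is not limited in that way.
- *That none of the listed terms is relevant.* Acute kidney injury plainly is, since creatinine is half of the primary outcome, and hypotension is plausible in patients on a furosemide infusion.
- *That the exclusions prove which harms the plan expects.* Section 2.1 also excludes sodium below 120, and the blood pressure limit is a 24-hour average used for eligibility.

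What the reply does not answer is ascertainment. A broad definition followed by an investigator-opinion filter allows these events to be recorded but does not ensure that they are recorded in the same way for every patient. Nor does it provide for counting them by arm.

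**Conclusion.** The point holds in this form: three foreseeable consequences of a sodium load are not predefined as adverse events or safety endpoints, while at least one named term has no evident link to the intervention. The data to derive sodium and blood pressure events are mostly collected, so the gap lies in definition, ascertainment and reporting. It can bias the adverse event comparison toward under-counting, by an amount the documents do not allow one to estimate. It does not affect the primary analysis.

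The conclusion assumes that the data dictionary does not already define these events. If it does, what remains is to bring the definitions into the protocol, reconcile the lists and plan the table by arm. The change is worth making because safety is a stated aim and the cost is very small.

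**What to change.** 1. Reconcile the adverse event lists in 6.1.3 and 7.1.1, including whether angioedema belongs and whether hypotension is to be qualified as sustained.
2. Add hypernatremia, hypertension and worsening congestion to all three lists as named adverse events of interest. The investigators should set the definitions and thresholds before any comparison by arm is seen.
3. State that sodium and blood pressure events will be derived from the values already recorded, by the same rule for every patient, and not only from patient report or investigator opinion.
4. In Section 5.4, state that all three events will be reported by arm as the number of patients and the percentage.

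The cost is protocol wording, a few eCRF fields and one extra safety table. No added visits, blood draws or patients are needed.
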